APPENDIX 4. Subject diary

▣ Protocol synopsis

Study title	A Pilot Study to evaluate efficacy and safety of Hydrophilic polyurethane foam dressing in patients with pressure ulcer
Clinical phase and design	Single-center, Randomized, 2-arms, open-label, phase 4 pilot study
Site	Seoul National University Hospital
Sponsor of the study	Mundipharma Pte Ltd
Study objectives	
This study aims to exploratively assess the efficacy and safety of the hydrophilic polyurethane foam in pressure ulcer patients.
 
As the primary objective, the percentage of completely healed patients and the time to complete healing will be assessed after applying the study device, Medifoam[®] or Betafoam[®], for 12 weeks to pressure ulcer patients. In addition, the pressure ulcer size reduction rate over 12 weeks will be evaluated.
 
# The definition of complete healing Epithelial tissue covering 100% of the study ulcer, no abrasion or ulceration, intact dermis and epidermis

Study indication	Pressure ulcer of the NPUAP Stage III
Inclusion and exclusion criteria	
<Inclusion criteria>
 
 1) Adults aged at least 19 years old as of the consent date 2) Pressure ulcer of the NPUAP(National Pressure Ulcer Advisory Panel) Stage III at screening 3) Pressure ulcer size of 3-100 cm² at screening 4) Written consent provided by the subject or representative 
(In case a subject has more than one pressure ulcers that meet all inclusion criteria, the largest one is selected as a target lesion.)
 
<Exclusion criteria>
 
 1) Any study ulcer of the NPUAP Stage I, II or IV 2) Diabetic ulcer or Venous ulcer (or stasis ulcer) 3) Past history of surgical treatment within 1 year or irradiation at the target pressure ulcer within 1 year 4) Hypersensitivity reaction to this product or povidone-iodine 5) Hyperthyroidism or thyroid disorder requiring drug treatment 6) Signs of a current underlying systemic infection (sepsis/bacterial infection/tuberculosis) or cellulitis or osteomyelitis 7) Type 1 diabetes 8) Current malnutrition 9) Heavy smoker: Current smoking level of ≥1 pack (20 cigarettes)/day of

	
tobacco
 
10) Drug or alcohol addiction
 
11) Requirement of immunosuppressants during the study or current chemotherapy or radiotherapy
 
12) Application of other investigational product/medical device within 1 month prior to the investigational device application (1d)
 
13) Pregnant or breastfeeding women
 
14) Other renal, hepatic, neurological, immunological disorder that may interfere with the wound healing process, at the discretion of the investigator
						

Target number of subjects
	
The target number of subject enrollment is 20 subjects, with 10 subjects per group.
 
This study has a purely exploratory goal so that no formal sample size calculation was conducted but it was planned to enroll 10 subjects per group as the minimum sample size to achieve study objectives from a scientific perspective.
 
 ✓ Medifoam group: 10 subjects ✓ Betafoam group: 10 subjects 
Even if a subject is withdrawn from the study, the subject will not be replaced.
						

Study method
	
<Overall study flow>
 
Subjects who consent to the study will be assessed for eligibility with screening tests. Subjects can have a 2-week screening period.
 
After screening, subjects who meet the inclusion/exclusion criteria will apply Medifoam[®] or Betafoam[®] for 12 weeks, after randomization. Targeted subjects are outpatient clinic or hospitalized patients. Subjects will make once weekly site visits.
 
  
 	Group A	Group B	
   
 Study device	Medifoam[®]	Betafoam[®]	
  
  
The diagram shows a horizontal timeline from 1d to 78d. Two parallel arrows represent the treatment periods for Group A (Medifoam) and Group B (Betafoam). Both arrows start at 1d and end at 78d, indicating a 12-week treatment period for both groups.
 
85d
 
<Dressing>
 
During the 12-week treatment period, dressing is performed twice weekly, and the End-of-Study visit is conducted 12 weeks after the investigational device application. However, an additional dressing change is allowed, depending on the
		Group A	Group B	Study device	Medifoam [®]	Betafoam [®]
	Group A	Group B					
Study device	Medifoam [®]	Betafoam [®]					

	
condition of the pressure ulcer, such as excessive exudates at the study ulcer. Nevertheless, the frequency of additional dressing is limited to twice per day. In case of further exceeding the limited additional dressing (twice per day), the change frequency should be recorded in the Case Report Form.
 
On weekly site visit days, the investigator(or clinical research coordinator) will change the dressing; on other occasions, the subject or guardian will perform self-dressing. The investigator(or clinical research coordinator) trains the subject or guardian on the dressing method at every visit.
 
<Early completion> Subjects who achieve complete healing of the target pressure ulcer within 12 weeks will have early completion. At the early completion visit, all tests scheduled for the Week 12 (End-of-Study) visit should be conducted.
 
<Efficacy assessment> Efficacy assessment is conducted for a total of 12 times at a 1-week interval, after the investigational device application (8d, 15d, 22d, 29d, 36d, 43d, 50d, 57d, 64d, 71d, 78d, 85d). At each efficacy assessment, the investigator(or clinical research coordinator) should take a digital photograph of the target pressure ulcer and retain it as a source document.


Investigational devices and application methods
	
[Investigational devices] Medifoam[®] (Mundipharma) Betafoam[®] (Mundipharma)
 
[Investigational device application methods]
 
 ① Carefully wash the target pressure ulcer with normal saline. ② After washing, wipe the study ulcer for drying with sterilized gauze, if necessary. During this process, take care not to irritate the study ulcer with the gauze. ③ Select a study device larger than the wound, open the product packaging, take out the device using tweezers, and remove the release film. Directly cover the wound with the foam side without the release film, paying attention to completely cover the wound. ④ If necessary, fix around the edge of this product with surgical tape or Band-Aid, taking care not to attach too tight to avoid skin irritation. ⑤ If there is a lot of exudate and a leak is likely to occur at the study ulcer, exchange the dressing more frequently than planned (twice weekly). 
[Standard treatment] ✓ Position change: The investigator(or clinical research coordinator) instructs the subject or guardian on the daily position changes. A subject who stays sitting or lying only should be instructed to change the position once every 2 hours.
 
[Prohibited concomitant medication]

	
 ✓ Any external use for pressure ulcer treatment (however, povidone-iodine may be allowed, if necessary.) ✓ Local antibiotics applied to the target pressure ulcer: However, in case of inevitable treatment, it can be applied. Other than local antibiotics, systemic antibiotics including injectable or oral preparations are allowed. ✓ Immunosuppressants ✓ Glucocorticoids. However, they may be administered when necessary, at the discretion of the investigator.

Assessment methods
	
1. Efficacy assessment
 
1) Endpoints of main interest
 
 ① Number of patients with complete healing# of ulcer within 12 weeks ② Time to complete healing of ulcer within 12 weeks ③ Pressure ulcer size reduction rate based on using a scale at each time point 
# The definition of complete healing Epithelial tissue covering 100% of the study ulcer, no abrasion or ulceration, intact dermis and epidermis
 
2) Other endpoints
 
 ① The PUSH(Pressure Ulcer Scores for Healing) reduction rate from baseline to each time point ② Dressing change frequency during the entire period ③ Number of subjects with Early completion due to complete healing during the study ④ Incidence of new infections at the pressure ulcer until Week 12 based on the CSSC 
2. Safety assessment
 
 ◆ Vital signs, laboratory tests ◆ Local adverse events at the target pressure ulcer: Erythema, edema, itching, flare, rash, other ◆ Other adverse events

Statistical analysis methods
	
Efficacy is assessed in the FAS while safety is evaluated in the SS.
 
 - SS(Safety set): Subjects who had at least 1 application of the investigational device and had at least 1 safety assessment - FAS(Full analysis set): Subjects who had at least 1 application of the investigational device and then had at least 1 available endpoints of main interest review 
1. Efficacy assessment
 
1) Endpoints of main interest
 
Of Endpoints of main interest, for subjects achieving complete healing within 12 weeks, present frequency and percentage.
 
For the time to 100% complete healing, analyze using the Kaplan-Meier method. Subjects not achieving 100% complete healing within 12 weeks will not be

	
considered for evaluation for end point of main interest. For the pressure ulcer size reduction rate by group, present mean and standard deviation.
 
2) Other endpoints For other endpoints, present mean and standard deviation for continuous variables ①, and frequency and percentage for categorical variables ②, ③, ④.
 
2. Safety assessment
 
1) Adverse events List all adverse events that occurred by group. Record the frequency of adverse events related or unrelated with the investigational device by group. For the number of adverse events and the percentage of subjects who had at least 1 adverse event, present the 95% confidence interval in each treatment group. Analyze adverse events separately for local adverse events at the target pressure ulcer and other adverse events.
 
2) Laboratory test findings For continuous data, present descriptive statistics (mean, standard deviation, median, minimum, maximum) by group and time point. In addition, tabulate the proportion of normal/abnormal results by time point in each group.
 
3) Vital signs For continuous variables, present descriptive statistics (mean, standard deviation, median, minimum, maximum) for the baseline and end-of-study test findings by group and time point.

--	--

▣ Schedule of study activities

Item \ Schedule	Screening		Treatment period																				Closing			
	1*	2*	3	4	5	6	7	8	9	10	11	12	13	14**												
	-14d~0d	1d 5d* (±1d)	8d (±1d)	12d* (±1d)	15d (±1d)	19d* (±1d)	22d (±1d)	26d* (±1d)	29d (±1d)	33d* (±1d)	36d (±1d)	40d* (±1d)	43d (±1d)	47d* (±1d)	50d (±1d)	54d* (±1d)	57d (±1d)	61d* (±1d)	64d (±1d)	68d* (±1d)	71d (±1d)	75d* (±1d)	78d (±1d)	82d* (±2d)	85d (±2d)	
Informed Consent Form	V																									
Demographic/medical history review	V																									
Physical examination	V	V	V	V	V	V	V	V	V	V	V	V	V	V	V	V	V	V	V	V	V	V	V	V	V	V
Vital signs ¹	V		V	V	V	V	V	V	V	V	V	V	V	V	V	V	V	V	V	V	V	V	V	V	V	V
Laboratory tests ²	V																									V
Height	V																									
Body weight	V							V																		V
Pregnancy test ³	V						V																			
Inclusion/exclusion criteria review	V	V																								
Randomization		V																								
Investigational device application ⁴		V	V	V	V	V	V	V	V	V	V	V	V	V	V	V	V	V	V	V	V	V	V	V	V	V
Investigational device prescription ⁵		V	V	V	V	V	V	V	V	V	V	V	V	V	V	V	V	V	V	V	V	V	V	V	V	V
Pressure ulcer assessment ⁶ (digital photograph taking, investigator's photo evaluation) - Ulcer size (Using a scale) - Complete healing status	V ⁷	V	V	V	V	V	V	V	V	V	V	V	V	V	V	V	V	V	V	V	V	V	V	V	V	V

Item	Schedule	Screening		Treatment period																		Closing					
		1*	2*	3	4	5	6	7	8	9	10	11	12	13	14**												
		-14d~0d	1d (±1d)	5d* (±1d)	8d (±1d)	12d* (±1d)	15d (±1d)	19d* (±1d)	22d (±1d)	26d* (±1d)	29d (±1d)	33d* (±1d)	36d (±1d)	40d* (±1d)	43d (±1d)	47d* (±1d)	50d (±1d)	54d* (±1d)	57d (±1d)	61d* (±1d)	64d (±1d)	68d* (±1d)	71d (±1d)	75d* (±1d)	78d (±1d)	82d* (±2d)	85d (±2d)
PUSH		V			V				V				V				V			V							V
Self-dressing training		V		V	V	V	V	V	V	V	V	V	V	V	V	V	V	V	V	V	V	V	V	V	V	V	V
Dressing change frequency review				V	V	V	V	V	V	V	V	V	V	V	V	V	V	V	V	V	V	V	V	V	V	V	V
Infection sign checklist ⁸ (CSSC)		V		V	V	V	V	V	V	V	V	V	V	V	V	V	V	V	V	V	V	V	V	V	V	V	V
Subject diary distribution ⁹		V		V	V	V	V	V	V	V	V	V	V	V	V	V	V	V	V	V	V	V	V	V	V	V	V
Subject diary return				V	V	V	V	V	V	V	V	V	V	V	V	V	V	V	V	V	V	V	V	V	V	V	V
Concomitant medication/treatment review	V	V		V	V	V	V	V	V	V	V	V	V	V	V	V	V	V	V	V	V	V	V	V	V	V	V
Adverse event review		V		V	V	V	V	V	V	V	V	V	V	V	V	V	V	V	V	V	V	V	V	V	V	V	V

* Visit 1 and Visit 2 can take place on the same day.

** Subjects who have complete healing during the study or are withdrawn from the study will have all tests scheduled for V14.

¥ Subject do not make a site visit but perform self-dressing.

† Except for Randomization visit, Home Health Care system through study coordinator will be used for those subjects who aren't able to make a visit during the treatment period. Physical examination and measuring weight may be exempt in case of replacing visit with Home Health Care.

- Blood pressure, pulse, body temperature measurement
- Laboratory tests: If test findings within 2 weeks prior to the consent date are available, they may be used instead of screening findings.
 - Hematology: WBC, RBC, platelet, WBC count, Hb, Hct
 - Blood chemistry: AST, ALT, ALP, creatinine, BUN, total bilirubin, glucose, protein, albumin, gamma GTP, TSH (TSH is conducted at screening only)
- Urine hCG pregnancy test is conducted only in women of child-bearing potential.
- The investigational device is changed twice weekly; additional changes are allowed depending on the pressure ulcer condition, without any limitation to frequency.
- Investigational devices for self-dressing are prescribed. Remaining investigational devices after use are returned at the next visit.

6. Pressure ulcer is evaluated comprehensively based on the investigator's photo evaluation. Photograph is taken using the same camera settings and environmental conditions for all subjects. For pressure ulcer assessment, record the following 2 results in the Case Report Form.
 - Ulcer size: Record the size of the residual pressure ulcer not achieving re-epithelization. The size is evaluated by a scale, using photographs that have been taken.
 - Complete healing status: Determine whether complete healing was achieved based on the ulcer size and the investigator's photo evaluation.(Re-epithelization: New epithelial tissue covering the pressure ulcer, with no exudate, transudate, or avascular tissue)
7. At screening, measure the ulcer size with a scale to confirm whether the size meets the inclusion criteria.
8. Infection signs are evaluated by the investigator using the CSSC (Clinical Signs and Symptoms Checklist). An infection is defined as a baseline condition of presence of 'Purulent exudates' or '2 or more symptoms of the CSSC'.
9. Record the number of body posture changes per day and the additional dressing change frequency.

▣ Abbreviations

ADE	: Adverse Device Effect
AE	: Adverse Event
ALT	: ALanine Transaminase
ALP	: ALkaline Phosphatase
AST	: ASpartate Transaminase
BUN	: Blood Urea Nitrogen
CRF	: Case Report Form
CSSC	: Clinical Signs and Symptoms Checklist
FAS	: Full Analysis Set
Hb	: Hemoglobin
Hct	: Hematocrit
ITT	: Intent to Treat
IRB	: Institute Review Board
MedDRA	: Medical Dictionary for Regulatory Activities
NPUAP	: National Pressure Ulcer Advisory Panel
PUSH	: Pressure Ulcer Scores for Healing
RBC	: Red Blood Cell
WBC	: White Blood Cell
γ-GT	: Gamma Glutamyl Transferase

1. Title and clinical phase of the study

A Pilot Study to evaluate efficacy and safety of Hydrophilic polyurethane foam dressing in patients with pressure ulcer

2. Name and address of the site

APPENDIX 3. Name and address of the site, names and titles of the principal investigator and sub-investigators

3. Names and titles of the principal investigator and sub-investigators

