Medifoam® is a dressing that can be used for burn, pressure ulcer, or serious wounds by providing a wet environment to the wound and thereby protecting the wound and promoting recovery. Medifoam® consists of 3 polyurethane layers and each plays a role of a protective layer, absorption layer, and wound-contacting layer. The protective layer protects the polyurethane layer from external infection and prevents infiltration of infectious microorganism, and maintains the optimal moisture vapor transmission rate(MVTR) to provide a wet environment to the wound (MVTR mean 811 g/m²/day). The absorption layer provides a wet environment to the wound, and immediately absorbs exudates from the wound. The product has the absorption capacity of ≥13.5-fold of the pre-absorption weight, and the moisture retention capacity of ≥6-fold. The wound-contacting layer has a mean 25-75 μm pore size (similar to fibroblasts and keratinocytes), and prevents newly formed epidermis from penetrating into the wound-contacting layer of the product or being removed while changing the dressing. As a result, damage to the recovering wound during the dressing change can be minimized, enhancing prompt wound recovery. Furthermore, as the layer is not adhesive to the wound, exudates can be absorbed effectively and the dressing can be changed while causing less physical and mental suffering.

Currently, Medifoam® is available as various formulations, including a foam type for a wound with oozing, a hydrocolloid type for relatively little oozing or exposed wound, and a liquid type for a wound requiring waterproof protection, so that they can be customized by wound type and lesion.

Meanwhile, Genewel Co., Ltd., the manufacturer of Medifoam®, newly developed povidone-iodine

containing polyurethane foam named Betafoam®. Povidone iodine(PVP-I) is known as a very effective local antibacterial agent and has been widely used as an effective disinfectant for various wounds. PVP-I has a broad antibacterial therapeutic window against bacteria, acid fast bacilli, fungus, protozoa, and viruses, and can be used to treat both acute and chronic wounds. Betafoam® is essentially a polyurethane foam dressing recognized for its effectiveness in various wounds. Based on characteristics of PVP-I and a foam dressing, Betafoam® is expected to support a routine wound healing process while also reducing the risk of wound infection.

<Summary of clinical study results>

(1) Medifoam N

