12.2.6 CSSC(Clinical Signs and Symptoms Checklist)

Infection signs are checked using the CSSC by the investigator at each visit. In case infection signs are suspected, laboratory tests and wound culture may be additionally conducted for confirmation. In case additional tests are performed, the result should be recorded in the Case Report Form.

According to [Baranoski, Elizabeth A. Ayello, Wound Care Essentials: Practice Principles], define an infection as the development of 'Purulent exudates' or '2 or more symptoms of the CSSC'.

At every visit after the study device application, evaluate the previous infection signs as well as any newly developing infection signs.

Clinical Signs and Symptoms Checklist	
Signs and symptoms	Check (+) if present

Increasing pain in the ulcer area
 
The patient reports increased level of peri-ulcer pain since the ulcer developed. Ask him to select the most appropriate statement for current level of ulcer pain from the following choices:
 
 1. I can't detect pain in ulcer area. 2. I have less ulcer pain now than I had in the past. 3. The intensity of the ulcer pain has remained the same since the ulcer developed. 4. I have more ulcer pain now than I had in the past. 
If the patient selects number 4, his pain is increasing. Write n/a if the patient can't respond to the question.
	

Erythema
 
The presence of bright or dark red skin or darkening of normal ethnic skin color immediately adjacent to the ulcer opening indicates erythema.
	

Edema
 
The presence of shiny, taut skin or pitting impressions in the skin adjacent to the ulcer
	

Clinical Signs and Symptoms Checklist	
Signs and symptoms	Check (+) if present
but within 4cm from the ulcer margin indicates edema. Assess pitting edema by firmly pressing the skin within 4cm of ulcer margin with a finger, release and waiting 5 seconds to observe indentation.	
Heat A detectable increase in temperature of the skin adjacent to the ulcer but within 4cm of the ulcer margin as compared to the skin 10cm proximal to the wound indicates heat. Assess differences in skin temperature using the back of your hand or your wrist.	

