Purulent exudates Tan, creamy, yellow, or green, thick fluid that's present on a dry gauze dressing removed from the ulcer 1 hour after the wound was cleaned and dressed indicates purulent exudate.	
Sanguinous exudates Bloody fluid that's present on a dry gauze dressing removed from the ulcer 1 hour after the wound was cleaned and dressed indicates sanguinous exudate.	
Serous exudates Thin, watery fluid that's present on a dry gauze dressing removed from the ulcer 1 hour after the wound was cleaned and dressed indicates serous exudate.	
Delayed healing of the ulcer The patient reporting no change, or increase in the volume or surface area of the ulcer, over the preceding 4 weeks indicates delayed healing. Ask the patient if the ulcer has filled with tissue or is smaller around than it was 4 week ago.	
Discoloration of granulation tissue Granulation tissue that is pale, dusky, or dull in color compared to surrounding, health tissue. Note variations of normal, beefy-red appearance of granulation tissue.	
Friable granulation tissue Bleeding of granulation tissue when gently manipulated with a sterile cotton-tipped applicator indicates friable tissue.	
Pocketing at base of wound The presence of smooth, nongranulating pockets of ulcer tissue surrounded by beefy red granulation tissue indicates pocketing.	
Foul odor The ulcer may have a putrid or distinctively unpleasant smell	
Wound breakdown Small open areas in newly formed epithelia tissue not caused by reinjury or trauma indicate wound breakdown.	

[Reference: Sharon Baranoski, Elizabeth A. Ayello, Wound Care Essentials: Practice Principles]

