## (2) Other endpoints

- ① PUSH reduction rate at each time point

$$\text{Reduction rate} = \frac{\text{PUSH score on 1d} - \text{PUSH score at each time point}}{\text{PUSH score on 1d}} \times 100\%$$

- ② Dressing change frequency during the entire study period

: Calculated as the additional dressing frequency beyond twice daily

- ③ Number of subjects with early completion due to complete healing during the study
- ④ Incidence of new infections at the pressure ulcer until Week 12 based on the CSSC

$$\text{Infection incidence} = \frac{\text{Number of subjects with at least 1 new infection}^{**} \text{ until Week 12, after the study device application}}{\text{Total number of subjects}} \times 100\%$$

(\*\* Infection: Presence of 'Purulent exudates' or 2 or more symptoms of the CSSC. However, for subjects with an infection at baseline, it is defined as development of an additional symptom other than those confirmed at baseline or recurrence of baseline-identified symptoms after being completely healed.)

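### The new-infection endpoint can count stalled healing with serous exudate, or local erythema with edema, as an infection, and no planned table shows which signs made each event

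*Protocol*

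**What the plan says.** The endpoint is fixed in Protocol 15.3 (2), item 4, repeated in Protocol 16.1 (2) and carried into SAP 7.1 (2): "Infection: Presence of 'Purulent exudates' or 2 or more symptoms of the CSSC". A subject counts once any such finding arises after device application and up to Week 12. For a subject already infected at 1d, an event is any sign not seen at 1d, or the return of a baseline sign that had cleared.

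Two other places word the same rule differently. Protocol 12.2.6 says to "define an infection as the development of 'Purulent exudates' or '2 or more symptoms of the CSSC" and takes this from a cited wound-care text. Footnote 8 of the schedule of activities says "An infection is defined as a baseline condition of presence of 'Purulent exudates' or '2 or more symptoms of the CSSC", which describes a state at baseline. For the new-infection endpoint, 15.3, 16.1 and the SAP govern.

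The checklist in 12.2.6 has 13 unweighted signs. Four matter here:
- Delayed healing: "The patient reporting no change, or increase in the volume or surface area of the ulcer, over the preceding 4 weeks indicates delayed healing".
- Serous exudate: "Thin, watery fluid that's present on a dry gauze dressing removed from the ulcer", judged one hour after the wound was cleaned and dressed.
- Erythema and edema next to the ulcer. The synopsis also has "Local adverse events at the target pressure ulcer: Erythema, edema, itching, flare, rash, other", and Protocol 12.2.7 has a matching list.

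Where infection is suspected, "laboratory tests and wound culture may be additionally conducted for confirmation", and the result goes into the CRF. Neither the endpoint nor any listed SAP table uses it. SAP 8 (2) applies Fisher's exact test to the endpoint. Table 0707 gives the number and rate per arm with a 95% interval. Tables 0705 and 0706 give the number of subjects with each sign at each visit.

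**The concern.** Protocol 5.1 expects Betafoam to "support a routine wound healing process while also reducing the risk of wound infection". Those are two separate expectations, healing and infection. The endpoint meant to address the second contains a sign that reflects the first. If one arm heals more slowly, its subjects report delayed healing more often, and some of them cross the two-sign threshold for that reason.

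A similar overlap exists with safety. New erythema and edema around the ulcer can be entered as local adverse events and also make the subject a new infection. No rule says how a finding on both lists is attributed.

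This pilot is meant to inform a further trial (Protocol 5.1). A difference in Table 0707 that arose from healing or from local reactions would be carried forward as a difference in infection, and the planned tables give no means of telling the two apart.

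**Working it through.** The documents give no expected infection rate or power for this endpoint, so there is no planned figure to reproduce. The check applies the written rule to sign patterns, counts combinations, and then gives an illustration on assumed rates.

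**Step 1: the rule applied.** The endpoint wording is presence of two signs, so a sign already there at 1d counts towards the two.

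| Signs at 1d | Signs at a later visit | New infection? |
|---|---|---|
| none | delayed healing | no |
| none | serous exudate + delayed healing | yes |
| none | erythema + edema | yes |
| serous exudate | serous exudate + delayed healing | yes |
| serous exudate | serous exudate + erythema | yes |
| serous exudate + delayed healing | unchanged | no |
| serous exudate + delayed healing | the same + erythema | yes |
| serous exudate + erythema | the same + delayed healing | yes |

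The last two rows use the clause for subjects infected at baseline. One further sign is enough for them, and that sign may be delayed healing itself.

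**Step 2: counting combinations.** Purulent exudate qualifies alone.
- Pairs among the other 12 signs: 12 × 11 / 2 = 66.
- Pairs made up only of the four signs above: 4 × 3 / 2 = 6.
- Pairs with at least one of the four: 66 − (8 × 7 / 2) = 66 − 28 = 38.
- Pairs left when serous exudate and delayed healing are not counted: 10 × 9 / 2 = 45, so 66 − 45 = 21 depend on one or both of them.

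These counts describe the breadth of the rule. They are not frequencies.

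**Step 3: weight of one subject.** With 10 per arm (Protocol 9), 1 / 10 = 10 percentage points.

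**Step 4: illustration, all rates assumed.** Take subjects not infected at 1d. Suppose delayed healing persists in 10% to 30% of them, and serous exudate is present at 30% to 70% of visits, independently over the 12 weekly assessments. The share who become events through this one pair is:
- Low: 0.10 × (1 − 0.7^12) = 0.10 × 0.986 = 0.099.
- High: 0.30 × (1 − 0.3^12) = 0.300.

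That is about 10% to 30%. It equals 1 to 3 subjects per arm only if all 10 are uninfected at baseline, and fewer otherwise.

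The four-week look-back lies wholly within treatment only from 29d (29 − 28 = 1). That leaves 9 visits, and the low end becomes 0.10 × (1 − 0.7^9) = 0.096, so the range hardly moves. If serous exudate instead persisted in 30% to 70% of subjects, unrelated to healing, the range would be 0.10 × 0.30 = 3% to 0.30 × 0.70 = 21%.

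**Step 5: what the tables allow.** Tables 0705 and 0706 give separate counts for each sign. Two subjects with serous exudate and two with delayed healing at one visit could be two, three or four people. The subjects who had both cannot be identified.

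**The case against.** The strongest reply is that the sponsor did not invent the rule. Protocol 12.2.6 takes it from a cited source, and whether a given sign is specific to infection is a clinical judgement that these documents cannot settle. That stands, and it is why the rule should remain the main definition. What the documents do settle is which patterns the rule admits and that two lists overlap.

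Several stronger readings are tempting and are not supported:
- *Non-healing or irritation is always reported as infection.* It can be. In a subject uninfected at baseline, delayed healing needs a second sign, and a pattern unchanged since 1d is no event.
- *Delayed healing is the size endpoint under another name.* It is reported by the patient over the preceding four weeks. The size endpoint is the investigator's measurement against 1d. An ulcer that shrinks and then stalls can show the sign and still have a positive reduction rate. The two are related, not identical.
- *Serous exudate is inevitable under an absorbent foam.* The sign is judged on dry gauze after cleaning, not on the worn dressing, and eligibility has no exudate criterion.
- *Skin reactions would tilt the comparison against Betafoam.* The side-effect list in Protocol 13.1 names neither erythema nor local edema (only pulmonary edema), and itching and rash are not CSSC signs. No direction can be claimed.
- *Over 12 visits nearly everyone would qualify.* That needs signs that vary independently from week to week. Weekly visits with a four-week look-back share about three weeks, so delayed healing cannot behave that way.

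It is also fair to say that Tables 0705 and 0706 already show purulent exudate by visit and arm. They also show every other sign, but not the combination within a subject. Finally, this is the fourth of the other endpoints in a 20-subject pilot. Protocol 16.2 plans no formal test, and the Table 0707 shell has no p-value column even though SAP 8 (2) names Fisher's test. That limits the weight of the point without removing it.

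**Conclusion.** The point holds in a limited form. As written, the endpoint can absorb stalled healing or a local skin reaction, and the planned output does not let a reader separate these from other events. For subjects infected at baseline the rule is looser still, since one further or returning sign is enough.

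The certain part of the size is 10 percentage points per subject in an arm of 10. How many subjects would be affected is unknown. The 10% to 30% illustration rests entirely on assumed sign rates, applies only to subjects uninfected at 1d, and falls to 3% to 21% if serous exudate is persistent. Neither range is an estimate for this trial.

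The main-interest endpoints are untouched. This is a reporting improvement worth making because it is cheap and because infection is one of the two benefits expected of Betafoam.

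**What to change.** In SAP 8 (2) and Table 0707:
- Keep the protocol definition as the first row.
- Add row (a): new infections with purulent exudate.
- Add row (b): new infections that still qualify when serous exudate and delayed healing are not counted. For subjects infected at baseline, the additional or recurring sign must likewise be one other than these two. State that baseline infection status itself stays as the protocol defines it. Of the six qualifying patterns in the table above, row (b) then keeps two: new erythema with edema, and erythema added to baseline serous exudate with delayed healing.
- List every event with its qualifying signs, the culture result where one was taken, and a flag if erythema or edema was also recorded as a local adverse event. Do not remove flagged events. A true infection may present with these signs, and removal would depend on how open-label investigators recorded them.
- State that a difference between arms is interpreted as infection only with reference to rows (a) and (b).

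The cost is two table rows, one listing and a few sentences, all from data already in the CRF. The added rows will hold fewer events, and row (b) departs from the cited two-sign rule, so it should be labelled as supplementary.
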